Administration of study drug will occur at Week 0, 12, 24 and 36, with an additional dose of rizankizumab made available at the Week 4 visit for those subjects that have not achieved a protocol defined response (defined as an improvement in tender and swollen joint count of \geq 20% compared with the baseline in Study 1311.5), provided the investigator believes this may be beneficial to the subject. Subjects who have not attained a protocol defined response at 2 consecutive visits at Week 12 visit or thereafter, will be discontinued from the OLE study. Other criteria leading to discontinuation of individual subjects in this trial are described in Section [5.4.1](#).

A \pm 4-day window is permitted around scheduled study visits after enrollment. If any visit has to be rescheduled, subsequent visits should follow the original visit date schedule.

Follow-Up Period

Subjects will have follow-up visits at Week 48 and 52 and a Follow-up Phone call 20 weeks after the last dose of study drug. All Follow-up Visit procedures are noted in [Appendix C](#). Subjects who discontinue study drug treatment early will need to attend an early End of Treatment (EOT) visit ideally within 2 weeks after the decision and preferably prior to the administration of any new therapies. An End of Study (EOS) visit 16 weeks after the last dose of study drug and a Follow-up Phone Call 20 weeks after the last dose of study drug is required to determine the status of any ongoing AEs/SAEs or the occurrence of any new AEs/SAEs (see [Appendix C](#) and Section [5.4.1](#)).

A schematic of the study design is shown below in [Figure 2](#).

Figure 2. Study M16-244 Study Design

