5.2.2 Exclusion Criteria

A subject will not be eligible for study participation if he/she meets any of the following criteria:

1. Female subject who is pregnant, breastfeeding or is considering becoming pregnant during study participation, including 20 weeks after the last dose of study drug is given.
2. Premature discontinuation of study drug in Study 1311.5 for any reason.
3. Use of a biologic treatment other than risankizumab since first dose of study drug in Study 1311.5.
4. Time elapsed is > 8 weeks since the Week 24 visit in Study 1311.5.
5. Active systemic infections during the last 2 weeks (exception: common cold) prior to randomization, as assessed by the investigator.
6. Anticipated requirement during the study or receipt of any live or attenuated vaccine since first dose administered in Study 1311.5.
7. Participation in another investigational study since first dose of study drug in Study 1311.5.
8. Current diagnosis of a major chronic inflammatory or connective tissue disease other than PsA (e.g., rheumatoid arthritis, systemic lupus erythematosus, ankylosing spondylitis, Lyme disease, gout) and fibromyalgia as assessed by the Investigator.
9. Use of any restricted medication as specified in this protocol or any drug considered likely to interfere with the safe conduct of the study, as assessed by the investigator, since first dose of study drug in Study 1311.5.
10. History of allergy/hypersensitivity to a systemically administered biologic agent or its excipients.
11. Chronic or relevant acute infections including HIV (human immunodeficiency virus), viral hepatitis and (or) active tuberculosis.
12. Any documented active or suspected malignancy or history of malignancy since first dose of study drug in Study 1311.5, except appropriately treated basal or squamous cell carcinoma of the skin or in situ carcinoma of uterine cervix.

13. Major surgery (including weight loss surgery), performed since first dose of study drug in Study 1311.5 or planned while study is ongoing as assessed by the investigator.

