Table 1. Clinical Laboratory Tests

Category	Test Name
Hematology	Hematocrit (Hct) Hemoglobin (Hb) Red Blood Cell Count/Erythrocytes Reticulocyte Count White Blood Cells/Leukocytes Platelet Count/Thrombocytes
Diff. Automatic	Neutrophils (relative count) Eosinophils (relative count) Basophils (relative count) Monocytes (relative count) Lymphocytes (relative count)
Diff. Manual (if Diff Automatic is abnormal)	Neutrophils, bands (Stabs) Neutrophils, polymorphonuclear (PMN) Eosinophils Basophils Monocytes Lymphocytes
Coagulation	Partial Thromboplastin Time (aPTT) Prothrombin time (INR) Fibrinogen
Enzymes	AST (GOT) ALT (GPT) Alkaline Phosphatase (AP) Creatine Kinase (CK) CK-MB, only if CK is elevated Gamma-Glutamyl Transferase (GGT/γ-GT) Lactic Dehydrogenase (LDH) Amylase Lipase
Electrolytes	Calcium Sodium Potassium Chloride Bicarbonate

Table 1. Clinical Laboratory Tests (Continued)

Category	Test Name
Substrates	Glucose BUN (blood urea nitrogen) Uric acid Creatinine eGFR Bilirubin Total Bilirubin Direct (if total is elevated) Bilirubin Indirect (if total is elevated) Troponin (Reflex, in case of elevated CK) Protein, Total Albumin C-Reactive Protein (CRP) (high sensitivity) Cholesterol, total Triglycerides LDL-Cholesterol HDL-Cholesterol
Urine Pregnancy test (only for women of childbearing potential) tested locally	Human Chorionic Gonadotropin in urine
Serum Pregnancy test (only if urine pregnancy test is positive)	Human Serum Chorionic Gonadotropin
Tuberculosis Screen	TB Skin Test (tested locally) or QuantiFERON®-TB Gold
Urinalysis (dipstick)	Urine Nitrite Urine Protein Urine Glucose Urine Ketone Urobilinogen Urine Bilirubin Urine RBC/Erythrocytes Urine WBC/Leukocytes Urine pH Urine creatinine

Table 1. Clinical Laboratory Tests (Continued)

Category	Test name
Urine-Sediment (microscopic examination, only if urinalysis abnormal)	Urine Sediment Bacteria Urine Cast in Sediment Urine Squamous Epithelial Cells Urine Sed. Crys., Unspecified Urine Sediment RBC/Erythrocytes Urine Sediment WBC/Leucocytes

Clinically relevant abnormal findings will be reported as baseline conditions or AE's. A clinically relevant value may be either in- or outside the reference range. Clinically relevant abnormal laboratory test results must be confirmed and should be repeated until normalization or stabilization or until an alternative explanation has been found.

Abnormal laboratory values will be also graded for intensity by using RCTC Version 2.0 criteria developed by OMERACT.¹¹

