- Subject is significantly non-compliant with study procedures which would put the subject at risk for continued participation in the trial in consultation with the AbbVie study designated physician.

If, during the course of study drug administration, the subject prematurely discontinues study participation, the procedures outlined for the early EOT visit must be completed, ideally within 2 weeks of the decision and preferably prior to the initiation of another therapy. However, these procedures should not interfere with the initiation of any new treatments or therapeutic modalities that the Investigator feels are necessary to treat the subject's condition. For subjects that prematurely discontinue, study drug will not be given at the early EOT visit and subjects should attend their EOS Visit 16 weeks after last study drug dose and complete a Follow-up Phone Call 20 weeks after the last dose of study drug to determine the status of any ongoing AEs/SAEs or the occurrence of any new AEs/SAEs (see [Appendix C](#)).

Subjects who prematurely discontinue from study drug will not be required to collect x-rays at a designated time point, unless they received a dose within the 16 weeks prior to the scheduled time point.

All attempts must be made to determine the primary reason for premature discontinuation. The information will be recorded on the appropriate eCRF page.

For subjects that are considered lost to follow-up, reasonable attempts must be made to obtain information on the final status of the subject. At a minimum, two phone calls must be made and one certified letter must be sent and documented in the subject's source documentation.

Subjects who discontinue the study prematurely will not be replaced.

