Appendix C. Study Activities

		Treatment				Follow-Up		Follow-up Phone Call
		V1	V2	V3	V4	V5 (EOT/Early EOT ^s)	V6	
Week	0^a	4^t	12	24	36	48	52	56
Day	1	29 ± 4	85 ± 4	169 ± 4	253 ± 4	336 ± 4	365 ± 4	392 ± 4
Informed Consent ^b	X							
Inclusion/exclusion criteria	X							
Medical/Surgical History ^c	X ^a							
Patient's Global Assessment of Disease Activity (VAS) (PtGA) ^d	X ^a	X	X	X	X	X	X	
Patient's Assessment of PsA Pain Intensity (VAS) ^d	X ^a	X	X	X	X	X	X	
HAQ-DI ^d	X ^a	X	X	X	X	X	X	
BASDAI ^{d,m}	X ^a			X	X	X	X	
SF-36v2 ^d	X ^a	X	X	X	X	X	X	
FACIT-F ^d	X ^a			X	X	X	X	
Vital Signs ^e	X ^a	X	X	X	X	X	X	
ECG ^e	X ^a			X		X	X	
Physical Exam ^e (c = complete, t = targeted)	X-c ^a	X-t	X-t	X-t	X-t	X-t	X-c	
Concomitant Therapy ^f	X ^a	X	X	X	X	X	X	

	Treatment					Follow-Up	
	V1	V2	V3	V4	V5 (EOT/Early EOT ^s)	V6	EOS (EOT/Early EOT + 16 Weeks)
Week	0^a	4^t	12	24	36	48	52
Day	1	29 ± 4	85 ± 4	169 ± 4	253 ± 4	336 ± 4	365 ± 4
Adverse Event Assessment ^g	X ^a	X	X	X	X	X	X
Tender Joint Count (TJC 68) ^h	X ^a	X	X	X	X	X	X
Swollen Joint Count (SJC 66) ^h	X ^a	X	X	X	X	X	X
PASI ^{h,u}	X ^a	X	X	X	X	X	X
BSA ^h	X ^a	X	X	X	X	X	X
Static Physician's Global Assessment for Psoriasis (sPGA) ^{h,u}	X ^a	X	X	X	X	X	X
Physician's Global Assessment of Disease Activity (PhGA) (VAS) ^h	X ^a	X	X	X	X	X	X
Leeds Dactylitis Index (LDI) ^h	X ^a	X	X	X	X	X	X
Leeds Enthesitis Index (LEI) ^h	X ^a	X	X	X	X	X	X
SPARCC ^h	X ^a	X	X	X	X	X	X
mNAPSI ^h	X ^a	X	X	X	X	X	X
mTSS (X-ray) ⁱ				X	X	X	X
Pregnancy Test ^j	X ^a	X	X	X	X	X	X
Safety Labs (Chemistry, Hematology, Urinalysis) ^{k,v}	X ^a	X	X	X	X	X	X

	Treatment						Follow-Up	
	V1	V2	V3	V4	V5 (EOT/Early EOT ^s)	V6	EOS (EOT/Early EOT + 16 Weeks)	Follow-up Phone Call
Week	0^a	4^t	12	24	36	48	52	56
Day	1	29 ± 4	85 ± 4	169 ± 4	253 ± 4	336 ± 4	365 ± 4	392 ± 4
hsCRP for DAS ^k	X ^a	X	X	X	X	X	X	
Blood Sample for PK ^{k,l}	X ^a	X	X	X	X	X	X	
Blood Sample for ADA Assay ^{k,l}	X ^a	X	X	X	X	X	X	
TB screening ^{k,n}					X		X ^r	
Local tolerability ^o	X	X	X	X	X	X		
Study drug administration	X	X ^p (additional)	X	X	X	X		
Monitoring for hypersensitivity reaction ^q	X	X	X	X	X	X		
Conclusion of Subject participation							X	

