Appendix C: Study Activities Table

	Treatment					Follow-Up		Follow-up Phone Call
	V1	V2	V3	V4	V5 (EOT/Early EOT)	V6	EOS (EOT/Early EOT + 16 Weeks)	
Week	0	4	12	24	36	48	52	56
Day	1 ± 4	29 ± 4	85 ± 4	169 ± 4	253 ± 4	336 ± 4	365 ± 4	365 ± 4
HBV DNA*	X			X			X	

* If subject had positive Hepatitis B Core Antibody or Hepatitis B Surface Antibody in Study 1311.5 and the reflex Hepatitis B virus DNA quantification level was undetectable at screening the HBV DNA level must be monitored at least every 6 months.

In the case of a tuberculosis-related adverse event, a supplemental case report form that provides additional information is be completed by the investigator or designee.

Local Requirements – Germany

Section 5.3.1.1 Study Procedures – X-Ray Assessments

The modified Total Sharp Score (mTSS) method, including distal interphalangeal joints, will be used to evaluate radiographic evidence of damage.¹⁹ X-rays of hands, wrists and feet. The x-rays will be performed at two time points (Weeks 24 and 48, detailed in [Appendix C](#)). Images will be read centrally for each subject in a random order and without knowledge of time point or subject identity. Subjects who prematurely discontinue from study drug will not be required to collect x-rays at each designated time point, unless they received a dose within the 16 weeks prior to the scheduled time point.

For subjects who have had an X-Ray performed within 2 weeks before the scheduled protocol X-ray assessment, no additional X-Rays should be performed.

Local Requirements – France**Section 5.2.1 Inclusion Criterion 2**

Women of childbearing potential must agree to use at least one of the following methods of contraception throughout the study including **20 weeks** after the last study drug dose is given:

- combined (estrogen and progestogen containing) hormonal birth control (oral, intravaginal, transdermal) associated with inhibition of ovulation initiated at least one month prior to study participation
- progestogen-only hormonal birth control (oral, injectable, implantable) associated with inhibition of ovulation initiated at least one month prior to study participation
- bilateral tubal occlusion/ligation
- intrauterine device (IUD)
- intrauterine hormone-releasing system (IUS)
- Vasectomized sexual partner(s) (the vasectomized partner should have received medical assessment of the surgical success and is the sole sexual partner of the trial participant).

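### Japan schedule: 196 days separate the Week 24 and Week 52 HBV DNA samples, longer than the six-month limit set by the table's own footnote

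*Protocol*

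**What the plan says.** The Japan part of Protocol Appendix D has its own version of the Appendix C activities table, with a single row for HBV DNA. The row is marked at V1 (Week 0, Day 1), V4 (Week 24, Day 169) and EOS (Week 52, Day 365), and at no other visit. Its footnote covers subjects who had hepatitis B core or surface antibody in Study 1311.5 and undetectable HBV DNA at screening. For them the "HBV DNA level must be monitored at least every 6 months".

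Appendix V prints this table before and after the amendment with the marks in the same three columns, so a column shift in the extracted text is unlikely. No other section schedules an HBV DNA sample between Weeks 24 and 52.

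The timing of EOS matters for subjects who stop early, and the protocol gives it in two ways:

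- Section 5.1 requires "An End of Study (EOS) visit 16 weeks after the last dose of study drug", and Section 5.4.1 agrees: "subjects should attend their EOS Visit 16 weeks after last study drug dose".
- The table header counts from a different event: "EOS (EOT/Early EOT + 16 Weeks".

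Section 5.1 also asks early stoppers to "attend an early End of Treatment (EOT) visit ideally within 2 weeks after the decision". That visit uses the V5 column, which has no HBV DNA mark.

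**The concern.** A schedule should by itself deliver the minimum that its own footnote makes mandatory. Here the marks are 24 weeks apart and then 28 weeks apart, and 28 weeks is more than six months.

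The footnote is a safety rule. It protects people with serological evidence of hepatitis B exposure while they receive a drug that, according to Section 3.4, may impair immune function. Section 5.2.3.2 also allows methotrexate up to 25 mg/week and systemic corticosteroid up to 10 mg/day of prednisone equivalent. Samples are drawn before dosing, so the long interval contains both the Week 24 and the Week 36 doses.

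A site that followed the marks exactly would take all three samples and still breach the footnote. Subjects who stop early could also go more than six months between samples.

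**Working it through.** **Inputs.** The visit days and windows come from the Japan table: Day 1, Day 169 ± 4, Day 253 ± 4 (Week 36), Day 336 ± 4 (Week 48) and Day 365 ± 4. Dosing at Weeks 0, 12, 24 and 36, with an optional Week 4 dose, comes from Section 5.1. The protocol does not convert six months to days. I take six calendar months, which run from 181 to 184 days depending on the start date.

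**The table's own days.** Day = 7 × week + 1 gives 1, 169 and 365 for Weeks 0, 24 and 52, as printed.

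**Completers**

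- Week 0 to Week 24: 169 − 1 = 168 days. This complies.
- Week 24 to Week 52: 365 − 169 = 196 days.
- Shortest gap the windows allow: 361 − 173 = 188 days. Longest: 369 − 165 = 204 days.
- Excess over 184 days: 196 − 184 = 12 (range 4 to 20). Excess over 181 days: 196 − 181 = 15 (range 7 to 23).

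**Early stoppers, EOS 16 weeks after the last dose (Sections 5.1 and 5.4.1).** EOS day = last dose day + 112.

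| Last dose | EOS day | Gaps between HBV DNA samples (days) |
|---|---|---|
| Week 0 (Day 1) | 113 | 112 |
| Week 4 (Day 29) | 141 | 140 |
| Week 12 (Day 85), no Week 24 sample | 197 | 196 |
| Week 24 (Day 169) | 281 | 168, then 112 |

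Only the Week 12 group without a Week 24 sample exceeds the limit.

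**Early stoppers, EOS 16 weeks after early EOT (table header).** EOS day = early EOT day + 112.

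- No Week 24 sample: gap = (EOT day + 112) − 1 = EOT day + 111. This is 184 at Day 73 and 185 at Day 74, so the limit is passed from Day 74 on. Day 80 gives 191 and Day 168 gives 279.
- Week 24 sample taken: gap = (EOT day + 112) − 169 = EOT day − 57. This is 184 at Day 241 and 185 at Day 242, so the limit is passed from Day 242 on. Day 250 gives 193.

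**The case against.** The strongest defence is that the footnote is itself binding and sits on the HBV DNA row. It sets a minimum frequency, and investigators must comply with the whole protocol, so a site reading the row should add a test. This stands in part: nothing forbids an extra sample, and one could be run from the Week 36 or Week 48 draw. But no visit is assigned to it, and a site could reasonably assume that the three marks were chosen to satisfy the rule printed beneath them.

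The second argument is size. The excess is about two weeks, it concerns a conditional subset in one country, and the documents do not say how many subjects qualify. Other safeguards apply:

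- Section 5.2.2 excludes "Chronic or relevant acute infections including HIV (human immunodeficiency virus), viral hepatitis".
- Appendix C schedules "Safety Labs (Chemistry, Hematology, Urinalysis") at Weeks 36 and 48, which covers ALT and AST.
- Section 5.3.1.1 adds that "Clinically relevant abnormal laboratory test results must be confirmed".
- Section 6.1.1.3 sets hepatic stopping rules.

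All of this stands and limits the risk. Liver enzymes are still not the viral test that the footnote demands.

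Third, the largest early-stopper gaps depend on a column header that two body sections contradict. That is fair. They are conditional figures, and the conflict over EOS timing is a separate matter that needs its own correction. The completer result does not depend on it, because V5 is also the Week 36 dosing visit.

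**Conclusion.** The point holds. For completers, the scheduled HBV DNA samples cannot meet the footnote under any timing the visit windows allow: the gap is 196 days nominally and 188 at the shortest, against at most 184. The only assumption is that six months means six calendar months.

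For early stoppers the answer depends on which EOS rule applies. Under the body text, only those last dosed at Week 12 without a Week 24 sample exceed the limit. Under the table header, some of those last dosed at Weeks 0, 4 or 24 could exceed it too.

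This is a local inconsistency in safety monitoring with a modest consequence, and it should be corrected. No planned analysis is affected: SAP Section 7.1 lists hepatitis testing only at screening.

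**What to change.** Add an HBV DNA mark in the V5 (EOT/Early EOT) column of the Japan table, using the blood draw already scheduled there.

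- **Completers:** 253 − 169 = 84 days (76 to 92 within windows), then 365 − 253 = 112 days (104 to 120).
- **Early stoppers without a Week 24 sample:** an early EOT on Day 168 gives 168 − 1 = 167 days. An early EOT two weeks after a Day 168 decision gives 182 − 1 = 181 days. EOS then follows after 112 days under the header. Under the body text, with the last dose on Day 85 and early EOT on Days 86 to 168, it follows after 111 down to 29 days.
- **Early stoppers with a Week 24 sample:** 252 − 169 = 83 days, or 266 − 169 = 97 days if early EOT comes two weeks after a Day 252 decision. EOS follows after 112 days under the header.

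The mark does not guarantee compliance for every early stopper, because the two-week target is only an ideal and Week 24 may fall as late as Day 173. A decision on Day 172 with early EOT on Day 186 gives 185 days from Day 1.

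A mark at Week 48 instead would serve completers (336 − 169 = 167 days, then 365 − 336 = 29 days) but not early stoppers. Loosening the footnote would remove the inconsistency only by weakening a safety requirement.

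The cost is one assay per affected Japanese subject with no extra visit. The text change is one mark, made by a protocol amendment that needs IEC/IRB approval under Section 9.1.

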Appendix E. Joint Assessment

Joint counts will be performed by assessor(s) who must be well trained and part of the site personnel. Whenever possible, the same evaluator should perform these assessments at all visits.

Number of Tender Joints:

The 68 joints assessed for tenderness include the 2 temporomandibular, 2 sternoclavicular, 2 acromioclavicular joints, 2 shoulders, 2 elbows, 2 wrists, 10 metacarpophalangeal, 10 proximal interphalangeal, 8 distal interphalangeal joints of the hands, the 2 hips, 2 knees, 2 ankles 2 mid-tarsal, 10 metatarsophalangeal, and 10 proximal interphalangeal joints of the feet.

Joints are to be scored as either tender (1) or not tender (0), replaced (9) or not assessed (99).

Number of Swollen Joints:

The 66 joints to be examined for swelling are the same as those examined for tenderness, however excluding both hip joints.

Joints are to be scored as either swollen (1) or not swollen (0), replaced (9) or not assessed (99).

Synovial fluid and/or soft tissue swelling but not bony overgrowth represents a positive result for swollen joint count.

Data will be recorded for tender and swollen joints (right or left side), i.e., a box (no, yes or not applicable) needs to be ticked for all joints. The total number of tender and swollen joints (right and left) will be automatically calculated in the eCRF.

Joint	Left		Right	
	Tender	Swollen	Tender	Swollen
Temporomandibular				
Acromioclavicular				
Sternoclavicular				
Shoulder [#]				
Elbow [#]				
Wrist [#]				
MCP1 [#]				
MCP2 [#]				
MCP3 [#]				
MCP4 [#]				
MCP5 [#]				
IP of the thumb [#]				
PIP of fingers 2 [#]				
PIP of fingers 3 [#]				
PIP of fingers 4 [#]				
PIP of fingers 5 [#]				
DIP of fingers 2				
DIP of fingers 3				
DIP of fingers 4				
DIP of fingers 5				
Hip*				
Knee [#]				
Ankle				
Mid-Tarsal				
MTP1				
MTP2				
MTP3				
MTP4				
MTP5				
IP of great toe				
PIP of toes 2				

Joint	Left		Right	
	Tender	Swollen	Tender	Swollen
PIP of toes 3				
PIP of toes 4				
PIP of toes 5				

* Hip will only be assessed for TJC (Tender Joint Counts), not for SJC (Swollen Joint Count).

Joints which will also count for DAS28-hsCRP evaluation.

Appendix F. PASI SCORE Definitions and Use

The PASI score is an established measure of clinical efficacy for psoriasis medications.³

The PASI is a tool which provides a numeric scoring for patients overall psoriasis disease state, ranging from 0 to 72. It is a linear combination of percent of surface area of skin that is affected and the severity of erythema, infiltration, and desquamation over four body regions.

The endpoints used are based on the percent reduction from baseline, generally summarized as a dichotomous outcome based on achieving over an X% reduction (or PASIX), where X is 50, 75, 90 and 100.

To calculate the PASI score, the four main body areas are assessed: **head (h), trunk (t), upper extremities (u) and lower extremities (l)**. These correspond to 10, 30, 20 and 40% of the total body area respectively.

The **area of psoriatic involvement** of these four areas (Ah, At, Au, and Al) is given a numerical value: 0 = no involvement, 1 = < 10%, 2 = 10 to < 30%, 3 = 30 to < 50%, 4 = 50 to < 70%, 5 = 70 to < 90%, and 6 = 90 to 100% involvement.

The **signs of severity, erythema (E), infiltration (I) and desquamation (D)** of lesions are assessed using a numeric scale 0 – 4 where 0 is a complete lack of cutaneous involvement and 4 is the severest possible involvement; scores are made independently for each of the areas, h, t, u and l and represents a composite score for each area. An illustration of judging erythema follows: 0 = no erythema, 1 = slight erythema, 2 = moderate erythema, 3 = striking erythema, and 4 = exceptionally striking erythema.

The PASI score is calculated according to the following formula:

$$\text{PASI} = 0.1(Eh+Ih+Dh)Ah + 0.3(Et+It+Dt)At + 0.2(Eu+Iu+Du)Au + 0.4(El+Il+Dl)Al$$

